##### Procedure:

If a subject did not receive the second trial vaccination the reason for this decision must be recorded in the eCRF. Visit 3 and Visit 4 are not required and the procedures below should be followed:

- Visit 5 procedures have to be performed 28 to 35 days after last vaccination

- FU 1 procedures have to be performed 182 to 210 days after last vaccination
- FU 2 procedures have to be performed 364 to 392 days after last vaccination.

If a subject from treatment Group 3 did not receive the second or booster vaccination the reason for this decision must be recorded in the eCRF. Visits 6, 7 and 8 are not required and the procedures below should be followed:

- FU 1 procedures have to be performed 182 to 210 days after last vaccination.
- FU 2 procedures have to be performed 364 to 392 days after last vaccination.

#### **4.2.6 Premature Discontinuation**

The trial may be discontinued prematurely for a subject at any time. The decision to discontinue the trial for a subject prematurely can be made by the investigator or by the subject. Reasons for discontinuing the trial prematurely may include, but are not limited to the following:

##### Criteria:

- Subject's request to discontinue prematurely (withdrawal of informed consent).
- Subject unwilling or unable to comply with trial requirements.
- Discontinuation due to an AE.
- Any reason that, in the opinion of the investigator, precludes the subject's further participation in the trial.

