## 1.5 Protocol Synopsis

Title Randomized, open-label Phase II trial to assess the safety and immunogenicity of MVA-BN® smallpox vaccine when increasing the number of injections compared to the standard regimen in immunocompromised subjects with HIV infection

[figure not shown]
---

Clinical phase Phase II

---

Sponsor Bavarian Nordic A/S

(b) (1) (A)

Coordinating Investigator

(b) (1) (A)

Number of sites and Country/ies Up to 10 sites in the USA

---

Vaccination dose and schedule

Group 1:  
One injection at Day 0 and Day 28 with 0.5 ml Modified Vaccinia Ankara Strain – Bavarian Nordic (MVA-BN®) smallpox vaccine containing at least  $1 \times 10^8$  Tissue Culture Infectious Dose 50% (TCID50) per ml (standard regimen)

Group 2:  
Two injections at Day 0 and two injections at Day 28 with 0.5 ml MVA-BN® smallpox vaccine each containing at least  $1 \times 10^8$  TCID50 per ml (double dose regimen)

Group 3:  
One injection at Day 0 and Day 28 with 0.5 ml MVA-BN® smallpox vaccine containing at least  $1 \times 10^8$  TCID50 per ml (standard regimen) and one booster injection at week 12 (booster regimen)

---

---

---

Route of administration	Each MVA-BN ® vaccination is administered subcutaneously (s.c.) in the upper arm.
Trial duration	Up to 75 weeks per subject
Sample size	90 (30 subjects per group)
Primary objective	To assess the safety of MVA-BN ® smallpox vaccine when increasing the dose or number of injections compared to the standard 2-dose regimen
Secondary objectives	To compare the immunogenicity and safety of three different vaccination strategies of MVA-BN ® smallpox vaccine
Primary endpoint	Occurrence, relationship and intensity of any serious and / or unexpected Adverse Event at any time during the trial.

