##### Criteria:

The following criteria should be checked prior to second/booster vaccination. If any are applicable, the subject should not receive any further vaccination(s):

- Any clinically significant cardiac sign and symptom (i.e. AESI) defined in [Section 8.1.2.3](#).
- An AE that, in the opinion of the investigator, makes it unsafe for the subject to receive a further vaccination. In this case, the appropriate measures will be taken.
- Anaphylactic reaction following the administration of any vaccine(s).
- Clinical need for concomitant or ancillary therapy not permitted in the trial, i.e.
  - Vaccination with any licensed live vaccine within 30 days prior or after trial vaccinations or any licensed killed vaccine within 14 days prior or after trial vaccinations
  - Start of chronic systemic administration (defined as more than 14 days) of > 5 mg prednisone (or equivalent) per day or any other systemic use of immune-modifying drugs.
  - Administration of immunoglobulins and/or any blood products.
- Use of any investigational or non-registered drug or vaccine other than the trial vaccine.
- Pregnancy
- Subject refuses to receive second vaccination.
- Any condition which contradicts administration of the second vaccination in the opinion of the investigator.

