##### Procedure:

If a subject discontinues prematurely, the reason for this decision must be recorded in the eCRF. If the subject is unable or not willing to attend all planned visits, every attempt should be made to perform at least a concluding safety visit. For WOCBP a pregnancy test should be performed during this safety visit. If the subject is not willing to undergo any further trial procedure (withdrawal of consent), "withdrawal of consent" needs to be documented as reason for premature discontinuation.

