### **8.2.5 Unsolicited AEs**

All intercurrent diseases reported when the investigator actively inquires the subject will be documented in the source and all required details (e.g. start and stop date, severity) will be assessed. Unsolicited AEs will be reported in the respective section of the eCRF and the subject's medical record.

AEs for Group 1 and 2 will be assessed and documented at all visits except FU 1 and FU 2 (i.e. Screening to Visit 5) and if ongoing at Visit 5, followed until resolution or until the FU 2 at the latest.

AEs for Group 3 will be assessed and documented at all visits except FU 1 and FU 2 (i.e. Screening to Visit 8) and if ongoing at Visit 8, followed until resolution or until the FU 2 at the latest.

SAEs/AESIs will be assessed and documented at all trial visits, including the FU 1 and FU 2. Ongoing AESIs which occurred after at least one vaccination will be followed up until resolution or achievement of stable clinical conditions. SAEs will be followed up until resolution or achievement of stable clinical conditions.

---

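### Sections 4.2.5 and 4.2.6 overlap for adverse events without saying which governs, and 4.2.6 has no provision for collecting new-onset SAEs and AESIs up to FU 2 after discontinuation

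*Protocol*

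**What the plan says.** **Stopping vaccination (Protocol 4.2.5).** One criterion for giving no further dose is "An AE that, in the opinion of the investigator, makes it unsafe for the subject to receive a further vaccination". A clinically significant cardiac sign or symptom is another. Observation continues: "FU 2 procedures have to be performed 364 to 392 days after last vaccination", and FU 1 is likewise required at 182 to 210 days.

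**Ending participation (Protocol 4.2.6).** "The trial may be discontinued prematurely for a subject at any time", by decision of the investigator or the subject. The reasons that may apply include "Discontinuation due to an AE", with no limit on type or grade. If the subject cannot or will not attend the planned visits, "every attempt should be made to perform at least a concluding safety visit". Contact at the FU 1 or FU 2 dates is not mentioned.

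**Events already begun (Protocol 8.2.5, repeated for AESIs in 8.2.7).** "SAEs will be followed up until resolution or achievement of stable clinical conditions". "Ongoing AESIs which occurred after at least one vaccination will be followed up until resolution" or stability. No exception is made for discontinued subjects.

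**Endpoint and analysis.** The primary endpoint is "Occurrence, relationship and intensity of any serious and / or unexpected Adverse Event at any time during the trial". AESIs are a secondary endpoint in the protocol; SAP 3.5.3 adds an AESI listing under the primary endpoint. That section lists SAEs from first injection to FU 2, and SAP 3.5.9 compares the groups descriptively on subjects with at least one SAE. The FAS (Protocol 9.3, SAP 3.2.1) keeps every vaccinated subject with any data.

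**The concern.** The two sections overlap for adverse events but lead to different observation. Under 4.2.5 the subject is seen for a year after the last dose. Under 4.2.6 the subject may leave, and nothing provides for learning of an SAE or AESI that starts afterwards. No rule decides between the two.

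The loss would be informative, because the subjects concerned are selected for having had an adverse event. The trial is open-label, so both the investigator and the subject know the regimen when the decision is made. The subject stays in the FAS denominator, and neither document plans a time-at-risk or truncated-follow-up analysis for safety. Missed events can only lower the observed SAE and AESI proportions.

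**Working it through.** **1. Which events can be lost.**
- Begun before discontinuation: not lost on paper, because 8.2.5 and 8.2.7 require follow-up to resolution or stability.
- New non-serious AEs after Visit 5 (Groups 1 and 2) or Visit 8 (Group 3): not collected from anyone (Protocol 8.1.2.1 and the schedule footnote), so nothing is lost in that period.
- New SAEs and AESIs between discontinuation and FU 2: collected under 4.2.5, not provided for under 4.2.6. In the long-term follow-up, this is the gap.

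**2. Observation time lost.** Inputs are the target weeks in Protocol 1.6 and the follow-up timing in 4.2.3 and 4.2.5.
- Groups 1 and 2, leaving at week 6 after dose 2: FU 2 is at week 56, so 56 − 6 = 50 weeks are lost; 50/56 = 89%.
- Group 3, leaving at week 6: the booster (week 12) has not been given. Under 4.2.5, FU 2 then falls 12 months after dose 2, which is week 4 + 52 = 56. The loss is again 50 of 56 weeks.
- Dose 1 only, leaving at day 28: 364 − 28 = 336 of 364 days; 92%.

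**3. The plan's own safety figure.** Protocol 9.2 and SAP 3.1 state at least 95% probability of detecting an AE with incidence 1 in 10, with 30 per group. The formula is P(at least one event) = 1 − 0.9^n.

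| Subjects observed | Probability |
|---|---|
| 30 | 95.8% (the stated figure reproduces) |
| 29 | 95.3% |
| 28 | 94.8% |
| 27 | 94.2% |

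The smallest n that reaches 95% is ln 0.05 / ln 0.9 = 28.4, rounded up to 29. The statement therefore tolerates the loss of one subject per group. The table treats the whole 1-in-10 incidence as arising after discontinuation. With a constant hazard instead, and two subjects leaving at day 28 of 364, the result is 1 − 0.9^28 × (0.9^(28/364))^2 = 94.85%, still just below 95%.

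With no events seen, the two-sided 95% Clopper-Pearson upper limit is 1 − 0.025^(1/n): 11.6% for 0/30 and 12.3% for 0/28.

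**4. Expected missed SAEs per group.** The documents give no dropout or SAE rate, so these inputs are assumed: 2 or 3 of 30 subjects discontinued at week 6, SAE risk to FU 2 of 5% to 15% in those subjects, and events uniform over 56 weeks. The formula is missed = k × risk × 50/56.
- Low end: 2 × 0.05 × 0.893 = 0.09.
- High end: 3 × 0.15 × 0.893 = 0.40.

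In relative terms, with a 5% risk in the remaining subjects, the observed proportion is too low by these amounts:
- k = 2, 5% risk: 1 − (28 × 0.05 + 2 × 0.05 × 6/56) / (28 × 0.05 + 2 × 0.05) = 1 − 1.411/1.500 = 6%.
- k = 3, 15% risk: 1 − (27 × 0.05 + 3 × 0.15 × 6/56) / (27 × 0.05 + 3 × 0.15) = 1 − 1.398/1.800 = 22%.

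The relative figures look large only because the base is 1.5 to 1.8 expected events per group.

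**The case against.** The strongest reply is that this is a wording gap with little practical effect. Several parts of it stand.

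- Section 4.2.6 is permissive and does not direct anyone to remove a subject who reacted. The decision may also be the subject's own.
- The AE criteria are not identical: 4.2.5 concerns AEs that make a further dose unsafe, whereas 4.2.6 names any AE.
- The triggering event is counted in the FAS. SAP 3.5.4 tabulates discontinuations with their primary reasons, and SAP 3.5.9 tabulates severe events and AEs leading to withdrawal from vaccination. A regimen with more AE-driven discontinuation would show it.
- The primary analysis is descriptive, so no test or margin is biased.
- Any two consent withdrawals in a group would have the same effect on the 95% figure, and no wording can prevent those.

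A reader might also infer that follow-up of the SAE or AESI that led to discontinuation is cut short. Sections 8.2.5 and 8.2.7 say otherwise. Nor is a single closing visit the stated procedure for everyone discontinued for an AE: it is the minimum for subjects unable or unwilling to attend.

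What the reply does not answer is the later period. For a willing subject whom the investigator discontinues, no further contact is described. Tabulating the reason for leaving does not recover an SAE that starts afterwards.

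**Conclusion.** The point holds as a gap in ascertainment. Sections 4.2.5 and 4.2.6 overlap for adverse events with no rule of precedence, and 4.2.6 allows, but does not make certain, the loss of new-onset SAEs (primary endpoint) and AESIs (secondary endpoint) before FU 2 in subjects selected for having had an AE.

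A subject leaving at week 6 loses about 50 of 56 weeks. A reader might put the Group 3 loss at 58 of 64 weeks, but that assumes a booster this subject has not received. The stated 95% detection probability is correct for 30 per group and fails at the second loss.

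The absolute effect is probably small: about 0.1 to 0.4 missed SAEs per group, less than half an event even at the upper end of the assumed rates. The documents do not support the stronger inference that the higher-dose or booster regimen would in fact look safer. They give no dropout or SAE rates by regimen, and AE-driven discontinuation is reported by group. A correction is justified because it is cheap and bears on a safety primary endpoint with 30 subjects per group.

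**What to change.** Reconcile 4.2.5 and 4.2.6 so that the protocol states which procedure applies when an adverse event occurs. Add to the 4.2.6 procedure that, for every vaccinated subject who has not withdrawn consent, whatever the reason for discontinuation, SAE and AESI status is sought at the FU 1 and FU 2 dates, by telephone or from records if the subject does not attend.

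Leave investigator and subject decisions on vaccination and participation unchanged. There is no need to remove investigator judgement or non-compliance as grounds for ending participation, because the gap lies in what is collected afterwards.

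The cost is protocol wording and at most two remote contacts per affected subject. The downside is that some SAE reports will come without an examination.

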##### Procedure:

If a subject discontinues prematurely, the reason for this decision must be recorded in the eCRF. If the subject is unable or not willing to attend all planned visits, every attempt should be made to perform at least a concluding safety visit. For WOCBP a pregnancy test should be performed during this safety visit. If the subject is not willing to undergo any further trial procedure (withdrawal of consent), "withdrawal of consent" needs to be documented as reason for premature discontinuation.

#### **4.3 Trial Duration**

The total duration of the trial for each subject including the screening period and Follow-up visits will be up to 75 weeks. The duration of the trial as a whole is dependent on the recruitment period.

#### **4.4 Data Safety Monitoring Board**

The DSMB is an independent board that oversees the safety of subjects participating in the trial. The members of the DSMB are independent, i.e. not involved as investigators in any MVA-BN® trials and have no direct or indirect financial interests in BN or the Contract Research

Organization (CRO) managing the trial. The primary responsibilities of the DSMB are to periodically review and evaluate the accumulated trial data for participant safety, trial conduct and progress, and make recommendations to BN and the Coordinating and PI(s) concerning the continuation, modification, or termination of the trial program. The DSMB considers trial specific data as well as relevant background knowledge about the disease, test agent, and subject population under trial. A separate charter describes in detail relevant operational procedures, communication pathways, roles and responsibilities of the DSMB.

If an event occurs which fulfills the trial halting rules the DSMB will review the event in a timely manner and give a recommendation to BN and the Coordinating Investigator and PI(s) to halt, resume or terminate the trial participation of the affected subject and/or the trial as a whole.

#### **4.5 Trial Halting Rules**

A temporary halting or termination for the trial as a whole can be decided by the DSMB in case of an occurrence of

- an SAE
- an unexpected Grade 3 or higher systemic reaction or lab toxicity ([Section 16.1](#); [Appendix I: Toxicity Scale for Laboratory Values](#))

with an at least reasonable possibility of a causal relationship to the administration of MVA-BN® smallpox vaccine, i.e. the relationship cannot be ruled out.

These parameters are not all-inclusive. Other AEs could occur that would trigger a DSMB review. Any member of the DSMB, any PI and/or the BN Drug Safety (DS) Officer could request a DSMB review based on any observation.

If an event fulfilling the trial halting criteria reaches the investigator's attention, the investigator has the liability to alert the responsible DS Department immediately (within 24 hours) and provide a comprehensive documentation of the event. Contact details of the responsible DS Department are provided in [Section 8.3.1](#).

### **5 Selection of Subjects**

Each investigator will keep a log of subjects screened for the trial, and provide the reason in case of exclusion. Information about every subject entering the trial will be documented in the eCRF.

#### **5.1 Recruitment Procedure**

Subjects will be recruited actively. Recruitment strategies, including IRB approved advertisements, will be evaluated by the Sponsor.

30 subjects will be enrolled in each group (90 in total).

---

After signing the ICF and HIPAA, subjects undergo screening procedures to check eligibility according to the inclusion/exclusion criteria. In the event of a screening failure secondary due to mild or limited acute illness or abnormal laboratory values, the subject may be re-screened after resolution of the event. Re-screening may require only an additional blood draw or a complete re-screening evaluation, depending on the circumstances of and the time interval from the initial screening failure (see also [Section 4.2.1](#)).

## 5.2 Inclusion Criteria

Please refer to trial protocol synopsis [Section 1.5](#).

## 5.3 Exclusion Criteria

Please refer to trial protocol synopsis [Section 1.5](#).

## 6 Investigational Medicinal Product

MVA-BN® smallpox vaccine is a highly attenuated live vaccinia virus which is administered subcutaneously. The packages and vials will be labeled according to the respective Product Specifications.

One vaccine dose has a virus titer of at least  $1 \times 10^8$  TCID50 /ml MVA BN® in 0.5 ml of the drug product.

For further details on MVA-BN® see current version of the Investigator's Brochure.

### 6.1 Production, Packaging and Labeling

The MVA-BN® bulk drug substance is produced at Bavarian Nordic A/S and the final drug product MVA-BN® is filled, formulated and labeled at the contract manufacturer (b) (1) (A) [REDACTED].

Addresses:

Bavarian Nordic A/S  
(b) (1) (A) [REDACTED]

(b) (1) (A) [REDACTED]

The packages and vials of liquid frozen (LF) MVA-BN® smallpox vaccine will be labeled with US IND labels.

### 6.2 Shipment, Storage and Handling

MVA-BN® smallpox vaccine will be shipped temperature controlled to the warehouse and from the warehouse to the CTS. At the CTS, the package is handed over to the personnel in charge of

vaccine preparation, e.g. the pharmacist. After receipt of vaccine, the personnel are responsible for proper storage of vaccine.

MVA-BN® smallpox vaccine is shipped and stored at  $-4^{\circ}\text{F} \pm 9^{\circ}\text{F}$  ( $-20^{\circ}\text{C} \pm 5^{\circ}\text{C}$ ) avoiding direct light. A vial should not be re-frozen once it has been thawed. Details on shipment, storage and handling of the LF formulation of MVA-BN® are provided in BN Standard Operating Procedure (SOP) (b) (1) (A) “Storage, Handling and Vaccination Procedures of Liquid Frozen MVA-BN® (IMVAMUNE ) and Recombinant MVA-Based Vaccines in Clinical Trials” listed in [Section 6.3](#).

### **6.3 Preparation, Administration and Dosage**

Details on vaccine preparation, administration and dosage of MVA-BN® smallpox vaccine are provided in SOP (b) (1) (A) entitled “Storage, Handling and Vaccination Procedures of Liquid Frozen MVA-BN® (IMVAMUNE®) and Recombinant MVA-Based Vaccines in Clinical Trials”.

### **6.4 Accountability and Disposal**

After receipt of the investigational medicinal product (IMP), the CTS personnel have the ultimate responsibility for distribution, proper storage and drug accountability. Records of receipt, inventory, use by each subject, return or disposal and temperature control must be maintained in the pharmacy file.

Used and unused vials should be stored in a safe place and remain the property of BN. The personnel of the respective CTS are responsible for ensuring adequate accountability of all used and unused IMP. This includes acknowledgement of receipt of each shipment of IMP (quantity and condition) and IMP accountability using an IMP inventory log. The IMP inventory log will document quantity of IMP received, quantity of IMP used for vaccination (including lot number, date dispensed, subject identification number and initials of the person dispensing the IMP) and quantity of IMP returned to BN or destroyed.

Additionally, the quantity of IMP returned to BN or destroyed must be documented on an IMP return/destruction form. If destruction at the CTS is agreed upon, material should be autoclaved or incinerated and discarded according to local regulations.

Furthermore, used syringes should be autoclaved or incinerated and discarded at the CTS according to local regulations.

## **7 Assessment of Immunogenicity**

The methods for collection, storage and handling of lab specimens for immunogenicity testing are specified in separate manuals, which will be provided to the investigators before enrollment commences. Additionally, training will be provided on the procedures during the investigator meeting and/or at the initiation visit.

## 7.1 Humoral Immunogenicity

Immunogenicity testing will be performed on samples obtained from subjects of all three groups on trial Visit 1, Visit 3, Visit 4, FU1 and FU 2. Further, immunogenicity testing will be performed on samples obtained from subjects of Group 3 on trial Visits 6 and 7. Blood samples obtained on vaccination visits (i.e., Visit 1, Visit 3 and Visit 6) will be drawn prior to vaccination.

Antibody responses to MVA-BN® smallpox vaccine will be measured using a vaccinia-specific ELISA and vaccinia-specific PRNT, both assays established and validated at BN. The immunogenicity analysis will be performed at BN. All personnel involved in immunogenicity testing will be blinded to subject randomization details.

The procedures for the analytical tests performed are outlined in [Sections 7.1.1](#) and [7.1.2](#) below. The SOPs, effective at the time of testing will be filed in the electronic Trial Master File.

### 7.1.1 ELISA

Details on the ELISA procedure can be found in SOP (b) (1) (A): “Automated ELISA for Detection of Vaccinia Specific Antibodies in Human Sera”.

The ELISA GMT is calculated by taking the antilogarithm of the mean of the log10 titer transformations. Titers below the detection limit are assigned the arbitrary value of 1.

The seroconversion rate is defined as the percentage of seroconverted subjects based on the total number of subjects included. Seroconversion is defined for initially seronegative subjects as appearance of antibody titers  $\geq$  detection limit. For subjects who are initially seropositive (i.e. with baseline [V1] antibody titers  $\geq$  detection limit) at least a doubling of the titer is needed to fulfill the definition of seroconversion.

